### Intervention

#### Development of the CIM2 intervention

The intervention elements in the CIM2 model have been inspired by the recommendations from the Medical Research Council guidance as described in the following four bullets [25] [24].

### Medical Research Council guidance for development of a complex intervention

- Identify and development of intervention: The project has undertaken a literature review in the field of organisation of care in multimorbidity to support the development of the intervention planned to be published in the autumn of 2021. The underlying development theory relies on the Chronic Care Model and uses methods as described for developing and evaluating complex interventions [25]. The interventions will be further developed based on information from participating researchers and health professionals.
- Assessment of the feasibility study and interventions: Assessment of the feasibility study and interventions has been reported previously [17].
- Implementation: the intervention is developed to impact everyday work in the general practice, in the municipality, and hospitals to a minimum. The GPs adopt a new type of consultation for a patient with complicated multimorbidity and both general practice, municipalities, and hospitals are part of the improved integrated care provision. Healthcare services and rehabilitation offered will remain within the already exciting guidelines. The GPs and hospitals are offered the opportunity for using cross-sectorial video conferences as described in the OK22 Agreement.
- Assessment of the complex intervention: This is described in the section “Evaluation” on page 4 in the project description.

### The intervention elements in the CIM2 model (Figure 2.)

- Training of healthcare professionals during a four-hour one-day course

The training program is developed in collaboration with The Danish College of General Practitioners. Healthcare professionals from general practice, nurses and physiotherapists from the municipalities, and healthcare professionals from the out-patient clinics participate in a training program. Healthcare professionals from general practice will receive training in project content, and methods to recruit and include patients (including informed consent). Further, does the education program offer training in the collection of patient data comprising the use of REDCap software for patient questionnaires.

[figure not shown]
For general practices allocated to the intervention group, the training also includes how to provide medical care for patients with complicated multimorbidity, case-based teaching, patient centred methods, structure and implementation of the extended overview consultation, and development of the care plan. Further, the training cover methods for improving collaboration and integration between general practice, the municipality, and the out-patient clinics using methods known from the national disease management programs.

- The extended overview consultation (in Danish “overblikskonsultation”) in general practice

The patient intervention starts with an extended overview consultation, lasting 45 minutes, with the GP, the patient (and maybe a relative), and the care coordinator. The consultation is based on the guidance for a patient-centred overview status for patients with multimorbidity published by The Danish College of General Practitioners [29]. The aim is to get an overview of the patient’s conditions, problems, and needs. The patient’s goals, preferences, and needs are identified, and treatments of the patient’s various conditions are prioritized. The GP decides who has the treatment responsibility for each condition. The patient’s resources for handling the chronic diseases are elicited, and if the patient is motivated, a referral to a relevant rehabilitation program in the municipality is planned [30]. The individual care plan is developed, covering planned activities in the three sectors that will take place within the 12-month intervention period. The GP will try to reduce the number of outpatient visits in the hospital or replace

outpatient visits with GP visits if the patient and the specialist agree. The GPs are reimbursed with 1.000 DKK. for the extended overview consultations

Figure 2. Central activities during the implementation and intervention phases of the study “Complex intervention for patients with complicated multimorbidity model version 2 (CIM2)” over time.

- The individual care plan

The individual care plan includes 6 themes: [29] 1) Listing of important diagnoses, 2) Overview of the patient's prescription drugs, 3) Prioritising the patients' treatment goals (using shared decision-making), 4) Development of a coordinated care plan with telephone follow-up and future visits, 5) Plan for potentially reducing the number of visits to hospital out-patient clinic for example by shifting hospital out-patient clinic visits to general practice, and 6) Referral to community-based rehabilitation. The care plan is printed for the patient.

- Care coordinator

General practice coordinates the planned patient care between general practice, the municipality, and the hospital, and follow-up on the execution of planned healthcare activities. The care coordinator function might be undertaken by the GP or the nurse in the practice. The practice plans the division of responsibilities and tasks in the project between the GP and the nurse.

- Follow-up activities

The follow-up activities include telephone calls to the patient by the care coordinator at relevant time intervals according to the severity of conditions and other important factors to follow up on planned activities with the patient. A second extended overview consultation takes place after 12 months.

- Integration of care elements

The individual care plan is shared electronically with the healthcare center in the municipality and with the outpatient clinics using the standard IT-communication tool provided by MedCom and a routinely used national standard in general practice, hospitals, and municipalities.

The GPs and hospitals are offered the opportunity for using cross-sectorial video conferences to plan the patient pathway as described in the OK22. This means that the GP arranges the conference when there is a professional indication for the conference. The GPs' participation in the videoconference is reimbursed.

The health professionals in the municipality provide information to the GP when patients have finished a rehabilitation program.

#### *The control group – usual care*

Patients with a GP allocated to the control group will receive usual care. To reduce the possibility of the Hawthorne effect, patients are offered a routine consultation conversation with a focus on patients everyday life with the nurse in general practice.

### **Evaluation and data collection**

The main evaluation objectives of the study will be addressed as follows:

#### *1) Assessing acceptability, workability and value for health professionals and patients*

This part of the evaluation will investigate how professionals and patients experience the model in terms of acceptability, workability and value. In particular the evaluation will assess whether the intervention supports patient-centred care and integrated care between general practice, hospital, and municipality. Also, this part of the evaluation will identify important facilitators and barriers for implementing the intervention in practice. These objectives will be achieved using a mix of qualitative and quantitative data.

At the end of the intervention, qualitative semi-structured interviews are performed with health professionals and patients. The interviews will include GPs and practice nurses from the seven practices in the intervention group as well as a number of healthcare professionals from the municipalities and hospitals who become involved in the cross-sectorial collaboration with the practices in the intervention group. Additionally, 15 patients will be interviewed.

The interviews will focus on the participants' experiences with the extended overview consultation and with the collaborative cross-sectorial elements of the intervention (especially video conferences and sharing of patient data). The interview guides will be informed by Normalization Process Theory (NPT) – a widely used theory to study the implementation of complex interventions in health care [31]–[33]. Following NPT, the interviews with health professionals will explore how they make sense of the intervention, how they engage with its various elements, how they operationalize the intervention in practice, and how they assess the value of the intervention. The interviews with patients will explore how the patients have experienced their treatment trajectory in terms of coherence and understanding of health care needs in relation to their expectations to integrated care. Also, the interviews with professionals and patients will explore their perceptions of facilitators and barriers to patient-centred and integrated care as well as their suggestions for how care can be improved. The interviews are recorded, transcribed, and subsequently analysed by thematic analysis and NPT.

Further, since the extended overview consultation is a key element in the intervention, video recordings of conducted intervention consultations are gathered and analysed to evaluate if the consultation supports the relational competencies of the GPs needed to ensure that the patients concerns and priorities are articulated and taken into account. A combination of interactional linguistics [34] and a

psychological interpretative framework [35] is used to analyse the relational aspects of the interactions. The video recordings will furthermore be used for evaluation in the conduction of video-stimulated recall interviews (VSRI) [36]. These interviews will elucidate how elements of the model affect the GPs' ability to work with relational competence, to help reduce work burden and prevent burnout. The analysis conducted for this evaluation will consist of Conversation Analysis and a psychological interpretive framework [35].

To supplement the qualitative data on the delivery of the intervention, quantitative data will be generated from the REDCap data collecting program (e.g., number of consultations delivered, number of care plans prepared, and the extent of cross-sectorial communications).

Based on the overall analysis, a proposal is prepared for the possible adjustments of the CIM2 model before the national trial. Subsequently, the results (including any adjustment proposals) are communicated to relevant stakeholders, who are given the opportunity to comment on the results, which may give rise to further adjustment to the CIM2 model before the national trial.

*2) Assessing the acceptability and feasibility of the cluster RCT study design and procedures*

The acceptability and feasibility of the study's tools and procedures for randomisation, recruitment, and data collection will be assessed through qualitative interviews with health professionals and patients supplemented by quantitative data generated by the study (e.g., variations in the number of recruited patients and questionnaire response rates). Patient characteristics according to age, gender, chronic conditions, medication, and care plans will be presented to the general practitioners, nurse care managers, and specialists to validate whether the identified and recruited patients are the "right" patients in need of the CIM2 model and the inclusion criteria are relevant.

Patient-reported questionnaire-data for Patient Assessment of Chronic Illness Care (PACIC), EuroQol-5 Domain (EQ-5D-5L), and Multimorbidity Treatment Burden Questionnaire (MTBQ).will be collected by electronic links by the REDCap software provided to patients at baseline, at 6-month follow-up, and at 12-month follow-up. If patients do not have IT-support at home, they will receive the questionnaires on paper.

The applicability of the following questionnaires will be evaluated from the completion rates of the questionnaires: 1) PACIC [37], [38], 2) EQ-5D-5L, and 3) MTBQ [39].

*3) Assessing and qualifying the preliminary power calculations of the PACIC questionnaire statistical estimates for the main RCT cluster study that is planned in the MM600 study*

Prior to the beginning of the pilot study, we performed a preliminary power calculation to get an understanding of the size of a future main RCT and whether this seemed realistic to use the PACIC questionnaire assessed from the statistical power of the questionnaire. To perform this power calculation, we made several assumptions. First, to our knowledge, no minimal important difference, which provides a "measure of the smallest change in the patient-reported outcome of interest that patients perceive as important", has been defined for the PACIC score. However, previous studies have reported a change in the PACIC score to be 0.36, to be clinically significant [39]. Hence, the power calculations are made towards detecting this difference between the two groups. Second, the power calculations take a potential Intraclass Correlation Coefficient (ICC) of 0.1 into account, which is an upper limit of values found through our literature search for similar studies [39]. Third, literature studies directed a choice of the total variation of 1. Fourth, we require that each clinic will recruit 25 patients and, with a random loss to follow up of 30%. From the stated assumptions, we base ourselves on the following random effects model for those not lost to follow up:

$$Y_i = \alpha_{Group(i)} + Z_{Clinic(i)} + \varepsilon_i, i = 1, \dots, n$$

where the variation of the random effect component  $Z$  reflects the ICC. Simulating the above model for 10.000 times per choice of the number of clinics in each group, with individually evaluated random loss to follow up, yields a power of 78%, 84% for 6 and 7 clinics in each group, respectively, based on a two-sided test at the level  $\alpha = 0.05$ . The uncertainty of these powers is found to be less than 1 percentage point, using the binomial formula. Thus, to obtain a power of 80% for detecting the specified difference  $\Delta$  from the random effects modeling, 7 clinics of 25 patients, i.e. 175 patients are needed in the intervention and control group.

The results from the pilot study will strengthen the validity of the estimates and clarify assumptions used in the power calculation. In particular, the results will clarify the need for implementing an ICC in the analysis of the main RCT, and if so, provide the power calculations with an estimated ICC value adapted to local conditions. Furthermore, the results from the pilot study will help to ascertain if 25 patients from each practice is a realistic number to include in the main RCT.

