the CIM2 model [17], [22]. The new CIM2 model includes improved training of healthcare professionals, strengthened identification of patients with complicated multimorbidity, adjustment of extended consultation according to the consultation model of DSAM, improved medical treatment, and strengthened integration of care services between healthcare organisations [17] [23].

The results from the first study of the CIM model [17] attracted the attention of policymakers in primary care, and the new collective agreement for general practice includes a plan to perform a large intervention project based on similar ideas and involving 600 GPs (hence labeled MM600 in the following). This has created a new critical potential for scaling up the elements from the CIM2 model at the national level. However, prior to large-scale implementation – and in accordance with the Medical Research Councils guidance on complex interventions [24] – the intervention must be pilot tested at a smaller scale in order to assess its functionality and effectiveness. For this purpose, we have designed the present pilot study named MM14 (since it includes 14 GPs). The MM14 pilot study will develop and strengthen the CIM2 model, and the results will be used to shape the MM600 national project.

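### The stated power of 78% and 84% for 6 and 7 clinics per arm does not follow from the protocol's own inputs, which give about 36% and 41% at most by formula

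*Protocol*

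**What the plan says.** The calculation is in the Protocol, Evaluation and data collection, part 3 (preliminary power calculations). The target difference rests on the statement that "previous studies have reported a change in the PACIC score to be 0.36, to be clinically significant". For clustering, "the power calculations take a potential Intraclass Correlation Coefficient (ICC) of 0.1 into account", a value described there as the upper limit found in the literature. For spread, "literature studies directed a choice of the total variation of 1". For cluster size, "we require that each clinic will recruit 25 patients and, with a random loss to follow up of 30" percent. The model has a group effect, a clinic random effect whose variance is set by the ICC, and a residual.

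From 10,000 simulations per scenario and a two-sided 5% test, the protocol reports that this "yields a power of 78%, 84% for 6 and 7 clinics in each group, respectively", with a simulation error below one percentage point. It concludes that, for 80% power, "7 clinics of 25 patients, i.e. 175 patients are needed in the intervention and control group". The section on randomization and blinding allocates practices, not patients, 1:1. The study design section uses the same size for the pilot: seven practices of 25 patients per arm.

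**The concern.** An ICC of 0.1 with 17 to 18 completers per clinic more than doubles the variance of the arm difference, so a study with seven clusters per arm should pay heavily for clustering. The stated powers show no such cost. They are higher than the same inputs give with independent patients.

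Objective 3 of the pilot is to assess and qualify this calculation for the main cluster trial, and the section says it was done to judge the size of that trial and whether PACIC is a realistic outcome. If the method is wrong, putting a better ICC estimate into it will not repair it, and the main trial could again be given too few clinics. The same section leaves open whether the main trial needs to allow for an ICC at all, and a calculation in which ICC 0.1 appears to cost nothing points the wrong way. In addition, the Background says the intervention should be "pilot tested at a smaller scale in order to assess its functionality and effectiveness", and the pilot has exactly the size this calculation yields. A reader could therefore take 84% as the pilot's power and over-interpret a null PACIC result.

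**Working it through.** **Inputs, all from the Protocol.** Difference 0.36; total variance 1 (the same if read as an SD); ICC 0.1, so clinic variance 0.1 and residual variance 0.9; 25 × 0.7 = 17.5 completers per clinic on average; two-sided α = 0.05; k clinics per arm, clinics randomised 1:1.

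**Formula.** Each clinic belongs to one arm only, so the clinic variance stays in the arm contrast:

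SE² = 2 × [0.1/k + 0.9/(17.5k)]

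Equivalently, the design effect is 1 + (17.5 − 1) × 0.1 = 2.65 and SE² = 2 × 2.65/(17.5k). Normal-approximation power is Φ(0.36/SE − 1.96). The small-sample version uses a noncentral t with 2k − 2 df.

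**Trying to reproduce the stated figures.**

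- k = 7: SE = √(2 × 2.65/122.5) = 0.208; 0.36/0.208 = 1.731; power = Φ(−0.229) = 40.9% (normal), 35.7% (t, 12 df). Stated: 84%.
- k = 6: SE = √(2 × 2.65/105) = 0.2247; 0.36/0.2247 = 1.602; power = Φ(−0.358) = 36.0% (normal), 30.5% (t, 10 df). Stated: 78%.

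The protocol's model was also simulated 10,000 times per scenario with Binomial(25, 0.7) completers per clinic. For 6 and 7 clinics per arm, power was:

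- 30.1% and 35.7%: t-test on clinic means
- 35.5% and 41.3%: z-test with known variances
- 38.4% and 43.6%: Wald z with estimated variance components

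The gap to the stated figures is at least 39 points under every one of these tests, so a simulation error below one point cannot explain it.

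**Other readings (normal approximation unless noted).**

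| Reading | 6 per arm | 7 per arm |
|---|---|---|
| Stated in the protocol | 78% | 84% |
| Stated inputs | 36.0% | 40.9% |
| One-sided test | 48.3% | 53.4% |
| No loss to follow-up | 39.4% | 44.7% |
| ICC 0.05 | 48.8% | 55.0% |
| Clinic variance 0.01 (0.1 read as an SD) | 67.6% | 74.2% |
| Unclustered t-test on clustered data (simulated) | 65.6% | 70.9% |
| ICC 0, variance 1 | 74.2% | 80.4% |
| Residual variance 0.9 only | 78.5% | 84.4% |

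Two of these matter most. With ICC 0, SE = √(2/122.5) = 0.128 at k = 7 and power is 80.4%. So with total variance 1, the stated loss and a two-sided test, no non-negative ICC reaches 84%. With the clinic variance dropped and only 0.9 kept, SE = √(2 × 0.9/122.5) = 0.121 and power is 84.4%. Simulating that case gives 77.9% and 84.2%, which matches the stated pair.

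**Ceiling.** With unlimited patients per clinic, SE = √(2 × 0.1/7) = 0.169, 0.36/0.169 = 2.13 and power is Φ(0.17), about 57%. At ICC 0.1, no cluster size gives seven clinics per arm 80% power.

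**What the inputs do support.**

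- Clinics for 80% power: k = (1.96 + 0.8416)² × 2 × (0.1 + 0.9/17.5)/0.36² = 18.3, so 19 per arm (81.4%, normal). The t calculation gives 20 per arm (81.4%). That is 19 × 25 = 475 to 20 × 25 = 500 patients per arm, not 175.
- Difference detectable with 80% power at 7 per arm: 2.80 × 0.208 = 0.58 (normal), about 0.63 (t).
- Expected 95% confidence interval half-width at 7 per arm: 2.18 × 0.208 = 0.45 (t, 12 df).

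**The case against.** The arithmetic itself cannot be defended, but four fair points limit what follows from it.

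- **The power is conditional.** ICC 0.1 is the protocol's upper-limit value. At ICC 0.05 power is 48.8% and 55.0%, and the clinics needed fall to (1.96 + 0.8416)² × 2 × (0.05 + 0.95/17.5)/0.36² = 12.6, so 13 per arm (normal). This stands: the corrected figures should be presented as conditional on the ICC. It does not rescue 78% and 84%, which exceed the value at ICC 0.
- **The cause is not known.** The simulation code is not in the document. Two other combinations that depart from the stated inputs come within 2 points: clinic variance 0.01 with no loss (80.0%, 85.6%), and a one-sided t-test without an ICC (78.3%, 84.3%). This stands: omission of the clinic variance is an inference from the numerical match. The error does not depend on the explanation.
- **The pilot's objectives do not include a PACIC test.** They are acceptability, feasibility and qualifying the power calculation, and the reference to effectiveness is background prose. This stands in part: the feasibility aims are not damaged. But qualifying this calculation is itself objective 3.
- **The main trial is unlikely to be run with 14 clinics.** It is described as involving 600 GPs, and the ICC will be re-estimated first. This makes direct adoption of seven per arm less likely. Re-estimating the ICC would not, however, reveal a fault in how the ICC is used.

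**Conclusion.** The concern holds. Under the protocol's own assumptions (difference 0.36, total variance 1, ICC 0.1, 25 patients per clinic, 30% random loss, two-sided 5%, practices randomised), power is 36% and 41% by the normal approximation for 6 and 7 clinics per arm, or 31% and 36% with a t reference, against the stated 78% and 84%. The overstatement is about 42 to 48 points. A true difference of 0.36 would be missed about 60% of the time or more at 7 clinics per arm if the ICC is 0.1. The statement that 7 clinics per arm suffice for 80% power is wrong: about 19 to 20 are needed under these inputs. Because the calculation is the subject of objective 3, the correction is essential, although the pilot's recruitment, conduct and feasibility aims are unaffected.

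**What to change.** 1. Check and re-run the simulation so that each of the 2k clinics has its own independent clinic effect, group is a between-clinic factor, and the clinic variance enters the standard error of the group difference. Name the test used.
2. Replace 78% and 84% with the corrected values: about 36% and 41%, or 31% and 36% with a small-sample t reference, which is the safer choice with 10 to 12 df.
3. Delete the conclusion that 7 clinics per arm give 80% power.
4. State that MM14, with 14 clinics unchanged, is not powered for a PACIC difference of 0.36. Give the detectable difference (about 0.58 to 0.63), and say that PACIC results will be reported as estimates with confidence intervals (expected half-width about 0.45).
5. Carry the corrected method into MM600 planning, with about 19 to 20 clinics per arm as the figure conditional on ICC 0.1, to be updated with the pilot's ICC estimate.

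The cost is a short simulation and one rewritten paragraph. No patients or clinics are added to the pilot. The stated power becomes less favourable.

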### **Aim of the pilot study**

The overall aim of this study is to evaluate important aspects of the “Complex intervention for patients with complicated multimorbidity model, version 2” (CIM2 model) in a pilot cluster-randomised controlled trial (RCT) before conducting a larger cluster RCT[25] being part of the research project described in the Agreement between PLO and Danish Regions 2022 (OK22).

The evaluation of the pilot study has three main objectives [26]:

- 1) To assess the acceptability, workability and value of the model as experienced by health professionals and patients. In particular, this includes:
  - a) Assessing if and how the model supports patient-centred care as experienced by patients and professionals
  - b) Assessing if and how the model supports integrated care between general practice, hospital, and municipality as experienced by patients and professionals
  - c) Identifying important facilitators and barriers for implementing the model in practice.
- 2) To assess the acceptability and feasibility of the cluster RCT study design and procedures;
- 3) To assess and qualify the preliminary power calculations of the Patient Assessment of Chronic Illness Care (PACIC) questionnaire statistical estimates for the main RCT cluster study that is planned in the MM600 project.

The results from the pilot study will be used to develop and strengthen the CIM2 model and the design of the MM600 project.

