### **Methods and design**

## Study principles and study design

The pilot study includes 14 general practice clinics – seven will be allocated to CIM2-group and seven will be allocated to perform usual care. Each practice will include 25 patients with complicated multimorbidity, thus, in total 350 patients. At 6 and 12 month intervention period, the patients' assessment of perceived patient-centred integrated care, health-related quality of life, and treatment burden will be measured in both groups (Figure 1).

Figure 1. The flow diagram illustrates the structure of the RCT pilot “A new care model for patients with complicated multimorbidity – A cluster-randomised pilot study in general practice, municipalities, and hospitals”. Patient Assessment of Chronic Illness Care (PACIC), EuroQol-5 Domain (EQ-5D-5L), Multimorbidity Treatment Burden Questionnaire (MTBQ).

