### *Randomization and blinding*

General practices in the designated municipalities are contacted with an invitation to participate in the study. If a general practice agrees to participate in the project, they will receive detailed study information. The 14 participating general practices will be randomised into either the intervention group providing care as described in the CIM2 model or the control group, providing usual care. The general practices will be randomly allocated, at an allocation rate of 1:1, by a computer program. To ensure concealment of allocation, a data manager from another organisation with no interest in the project will provide the information of the randomization to the general practice draw and will be responsible for a randomization list, which will be available to the investigator. Due to the nature of the study, the general practices and the patients cannot be blinded.

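### Whether the main cluster trial accounts for clustering is left to the pilot result, which cannot settle it

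*Protocol*

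**What the plan says.** The protocol's section *Evaluation and data collection*, part 3 (qualifying the preliminary power calculations), ends by listing what the pilot will deliver to MM600. It states that "the results will clarify the need for implementing an ICC in the analysis of the main RCT" and adds that, where the need is found, the pilot will "provide the power calculations with an estimated ICC value adapted to local conditions". Both the word for need and the condition attached to supplying a value make clustering conditional on what the pilot finds. No criterion for need is given, and nowhere does the protocol say that practice will be accounted for in any case.

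Other parts of the protocol treat clustering as a given:

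- *Aim of the pilot study* describes the present trial as one run "before conducting a larger cluster RCT".
- *Randomization and blinding* makes practice the unit of allocation in the pilot: "The general practices will be randomly allocated, at an allocation rate of 1:1, by a computer program".
- The power section sets an ICC of 0.1, "which is an upper limit of values found through our literature search for similar studies", and continues: "we base ourselves on the following random effects model for those not lost to follow up". That model contains a clinic effect.

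**The concern.** In a cluster-randomised trial the need to account for the cluster follows from how treatment was allocated, not from an estimate. A pilot can properly inform how large the ICC is, and so how many practices the main trial needs. It cannot license an analysis that treats patients as independently randomised.

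The sentence matters because qualifying the power calculation for MM600 is the third stated objective of the pilot, so it defines one of the pilot's outputs. If a low estimate were read as showing no need, the MM600 confidence intervals would be too narrow and its test would exceed 5%. A low or non-significant estimate is also quite likely when clustering is real, because 14 clinics carry little information about between-clinic variance.

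**Working it through.** **Inputs from the protocol.** 14 clinics, 7 per group; 25 patients recruited per clinic; 30% random loss, so m = 25 × 0.7 = 17.5 analysed per clinic and 14 × 17.5 = 245 in all; ICC 0.1 as an upper limit; two-sided 5% test.

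**Assumptions, not in the protocol.** ICCs of 0.01, 0.03 and 0.05; both decision rules in step 3; MM600's cluster size and number of clinics.

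**The plan's own figure.** The stated powers of 78% and 84% (6 and 7 clinics per group) do not follow from the stated inputs. With a design effect of 1 + 16.5 × 0.1 = 2.65, the effective n per group for 7 clinics is 122.5/2.65 = 46.2, which gives about 41% power by normal approximation (36% for 6 clinics). That is a separate matter, and nothing below relies on those powers.

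**Step 1: what the pilot can say about the ICC.** Take a one-way analysis of variance of clinics within groups, with 14 − 2 = 12 and 245 − 14 = 231 degrees of freedom. An ICC estimate corresponds to F = 1 + m × ICC/(1 − ICC). The exact 95% limits are F/2.001 and F/0.3626 (the 97.5% and 2.5% points of F on 12 and 231 df), transformed back by (F − 1)/(F − 1 + m).

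- Estimate 0: F = 1. Upper limit F = 1/0.3626 = 2.758, so ICC = 1.758/19.258 = 0.091. The lower limit is −0.03.
- Estimate 0.10: F = 1 + 17.5 × 0.1/0.9 = 2.944. Limits F = 1.471 and 8.120, so ICC from 0.471/17.971 = 0.026 to 7.120/24.620 = 0.289.
- With no loss (m = 25), the upper limit for an estimate of 0 is 0.065.

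**Step 2: type I error if practice is dropped.** The variance of the group difference is understated by the design effect DE = 1 + 16.5 × ICC, and the true type I error is 2 × (1 − Φ(1.96/√DE)).

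**Step 3: averaging over pilot results.** The average is P(drop) × (error if dropped) + (1 − P(drop)) × 5%. Rule A drops practice when the pilot's 5% F test is not significant; rule B drops it only when the ICC estimate is zero or below.

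| True ICC | DE | Error if dropped | P(drop), A | Average, A | P(drop), B | Average, B |
|---|---|---|---|---|---|---|
| 0.01 | 1.165 | 6.9% | 0.884 | 6.7% | 0.401 | 5.8% |
| 0.03 | 1.495 | 10.9% | 0.690 | 9.1% | 0.201 | 6.2% |
| 0.05 | 1.825 | 14.7% | 0.486 | 9.7% | 0.100 | 6.0% |
| 0.10 | 2.65 | 22.9% | 0.167 | 8.0% | 0.019 | 5.3% |

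Worked line, ICC 0.05: 1.96/√1.825 = 1.451, two-sided tail 14.7%; rule A gives 0.486 × 14.7% + 0.514 × 5% = 9.7%.

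**Step 4: does a larger trial help?** DE depends on cluster size and ICC, not on the number of clinics. Simulating a t test that ignores clinic (25 recruited, 30% random loss) at ICC 0.01, 0.05 and 0.10 gave 7.4%, 13.5% and 22.6% with 7 clinics per group (4,000 runs), and 8.1%, 15.1% and 22.3% with an assumed 150 per group (2,000 runs). In a further simulation with 7 clinics per group, a cluster-level test stayed at 4.7% to 5.4%.

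**The case against.** The strongest reply is that the sentence is loosely worded and is really about sample size. It sits in a section on power calculations, the clause that follows says the pilot will "provide the power calculations with an estimated ICC value adapted to local conditions", and a planning model with a clinic effect shows that the authors know about clustering. This reading is possible. However, the sentence names the analysis of the main trial and the power calculations separately. On the milder reading the type I error figures fall away, but the conditional remains unsound: leaving the ICC out of the sample size when it is truly 0.1 would understate the number of patients by the factor 2.65, and 12 degrees of freedom are no basis for doing so.

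It can also be said that MM600 will have its own protocol, that nothing here commits it to ignoring practice, and that both decision rules above are assumed. All of that stands. Under the milder rule the average error is only 5.3% to 6.2%, and the 22.9% applies only if practice is dropped when the ICC is 0.1. The 0.09 limit is the two-sided one at 17.5 patients per clinic; a one-sided 95% limit is 0.070, and with no loss the two limits are 0.065 and 0.050. Even the smallest of these leaves room for an ICC that matters: at 0.05 with 25 analysed per clinic, DE = 1 + 24 × 0.05 = 2.2 and the error with practice dropped is 18.6%.

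Finally, practice is named explicitly as the unit of randomisation only for the pilot. For MM600 the protocol says cluster RCT, and its power section speaks of patients per practice in the main RCT, which points to practice as the cluster.

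**Conclusion.** The concern holds. The sentence makes an obligation of the design conditional on an estimate, and the pilot is too small to show that clustering is negligible: an ICC estimate of zero is compatible with values up to about 0.09 (0.065 with no loss to follow-up). If practice were dropped from the MM600 analysis at 17.5 patients per clinic, the true type I error would be between 6.9% (ICC 0.01) and 22.9% (ICC 0.1). Averaged over pilot results it would be 6.7% to 9.7% under the F-test rule, or 5.3% to 6.2% if practice were dropped only for an estimate of zero or below. The smaller ICCs, both rules and MM600's size are assumptions. The conclusion that clustering must be accounted for depends on none of them, only on MM600 being a cluster-randomised trial as the protocol describes it. The pilot's own conduct is unaffected, so this should be corrected but does not threaten the pilot.

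**What to change.** Replace the sentence with wording such as:

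> The main RCT analysis will account for practice, the unit of randomisation, regardless of the pilot ICC estimate. The pilot will report the PACIC ICC with its 95% CI to inform the main trial's power calculation, with power shown across that interval.

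If MM600 is to randomise a unit other than practice, name that unit instead. The cost is a change of wording, with no change to how the pilot is run. The one drawback is that power shown across a wide ICC interval may look less favourable for the main trial than power at a single value.
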